8.4 Adequacy of Protection Against Risks

8.4.1 Protections against Risk

Participants will be counseled on possible side effects following vaccination and followed closely during the first 8 days post-vaccination for assessment of local and systemic reactogenicity, solicited and unsolicited adverse events (AEs), serious AEs (SAEs), concomitant medication use, and unscheduled medical care. All participants will be monitored in a sitting or lying position for at least 20 minutes following vaccinations to help prevent fainting, and injuries caused by a fall. Participants with a prior history of any precaution or contraindication to either IIV or RIV will be excluded from study enrollment.

Every effort possible will be made to keep information about participants confidential. Computerized participant information will be kept in password protected files on secured servers. Paper case report forms will be kept in locked files belonging to the study

personnel. Any publications resulting from this work will not contain any identifiable participant information.

8.4.2 ClinicalTrials.gov Requirements

The project is registered on ClinicalTrials.gov (NCT03969641). It is the responsibility of the lead site for creating, maintaining, and uploading pertinent information regarding the study as required by 45 CFR 46.116(h) to ClinicalTrials.gov. The lead site will post their IRB-approved informed consent within the study's record on ClinicalTrials.gov. Contributing sites will be responsible for providing the lead site with any changes to their site's information as applicable.

9.0 Human Participants

In obtaining and documenting informed consent, the Investigator and study team will comply with the applicable regulatory requirements, Good Clinical Practices, and ethical principles. The written informed consent form must be signed and dated by the study participant prior to initiation of any study activities.

9.1.1 Vulnerable Subjects Research

Vulnerable subjects

This study proposes to include pregnant women and neonates.

Pregnant women

RIV4 and IIV4 are FDA licensed vaccines and are recommended by the CDC and ACOG during pregnancy, however the risks for both vaccines are listed in section 8.3.

The specific procedures to be performed as part of this study are limited to minimal blood draw (< 35mL over a 4-week period), and other non-invasive procedures that are commonly performed during routine physical exams and are considered safe for pregnant women. These procedures do not pose greater than minimal risk to the fetus.

This study will involve only those women who have given their free and informed consent in accordance with 45 CFR 46.116 and has the prospect of direct benefit to both the mother and infant. Randomization of vaccine administration provides minimal risk to the participant and fetus as IIV vaccines are routinely given during pregnancy and do not go beyond the scope of standard of care. The small amount of blood that will be drawn during the duration of pregnancy (up to 30 ml) are considered safe and are not expected to cause any harm to the baby. No inducement, monetary or otherwise, will be offered to terminate a pregnancy. Individuals engaged in the research will have no part in any decisions as to the timing, method or procedures used to terminate a pregnancy, or in determining the viability of a neonate.

Infants

Identifiable private information will be collected about the infants at the time of delivery. Significant infant complications identified during the delivery visit will be followed up to 90 days of life.

Mothers will be informed about the infant data collection at the time they consent for the study, and thus, the consent form for pregnant women will also serve as the parental permission for including the infant as a participant after delivery.

REFERENCES

## 1 INTRODUCTION

This document describes the statistical procedures that will be utilized for the CISA protocol Safety and Immunogenicity of Pregnant Women Receiving Quadrivalent Recombinant Influenza Vaccine (RIV4) versus Quadrivalent Inactivated Influenza Vaccine (IIV4) that was approved on August 10, 2020. This statistical analysis plan (SAP) describes the methods of statistical analysis. The initial draft SAP (Version 0.1) was developed prior to any data being analyzed in order to avoid bias. Any subsequent changes that occur to the study protocol and requires changes to the analysis procedures will be documented in the SAP (both draft versions (0.X) and the final version (X.0)). Table 1 below will be used for tracking of changes to the SAP. In this study adult pregnant women  $\geq 18$  years at  $\leq 34$  weeks gestation are randomized 1:1 to receive either RIV4 (Flublok® quadrivalent recombinant influenza vaccine) or IIV4 (quadrivalent inactivated influenza vaccine) using a permuted block randomization scheme stratified by study site (Duke, Cincinnati, Boston).

Table 1. Statistical Analysis Plan Versions

Version	Date of Approval	Major Changes from Prior Version
0.1	TBD	NA
0.2	TBD	Removed language regarding stratification by gestational age because an error in setting up REDCap lead to drawing from only the <20 weeks randomization block in the 2019-20 influenza season.

## 2 PROTOCOL OBJECTIVES

### 2.1 Primary

- a) PO1: To compare the proportions of adverse birth outcomes in pregnant women vaccinated with RIV4 versus IIV4.

*Research hypothesis: The proportion of pregnant women with adverse birth outcomes will be noninferior (not higher) after receipt of RIV4 compared to IIV4.*

### 2.2 Secondary

- a) SO1: To compare proportions of preterm birth after RIV4 versus IIV4 vaccination.
- b) SO2: To compare proportions of combined fetal and neonatal death after RIV4 versus IIV4 vaccination.
- c) SO3: To compare proportions of spontaneous abortion after RIV4 versus IIV4 vaccination.
- d) SO4: To compare proportions of moderate/severe solicited reactogenicity events in pregnant women vaccinated with RIV4 versus IIV4.

### 2.3 Exploratory

- a) EO1: To compare and describe serious adverse events (SAE) in pregnant women vaccinated with RIV4 versus IIV4.

- b) EO2: To compare proportions of adverse pregnancy and birth outcomes of clinical interest after RIV4 versus IIV4 vaccination.
- c) EO3: To compare and describe health outcomes through 90 days of life in infants born to women after RIV4 versus IIV4 vaccination.
- d) EO4: To compare maternal immune responses to influenza antigens after RIV4 versus IIV4 vaccination.
- e) EO5: To compare cord blood antibody levels for influenza antigens after RIV4 versus IIV4 vaccination.

### **3 STUDY ENDPOINTS**

#### **3.1 Primary**

- a) POM1: Proportions of adverse birth outcomes in pregnant women vaccinated with RIV4 versus IIV4.  
Adverse birth outcome is a composite of occurrence of at least one of the following: preterm birth, spontaneous abortion, fetal death, or neonatal death.

#### **3.2 Secondary**

- a) SOM1: Proportions of preterm birth after RIV4 versus IIV4 vaccination.
- b) SOM2: Proportions of combined fetal and neonatal death after RIV4 versus IIV4 vaccination.
- c) SOM3: Proportions of spontaneous abortion after RIV4 versus IIV4 vaccination.
- d) SOM4: Proportions of pregnant women with moderate/severe solicited reactogenicity events (local and systemic) within 8 days after vaccination with RIV4 versus IIV4.

#### **3.3 Exploratory**

- a)
  - 1. EOM1.1: Frequency and descriptions of serious adverse events in pregnant women vaccinated with RIV4 versus IIV4 during the 42 days after vaccination.
  - 2. EOM1.2: Frequency and descriptions of serious adverse events in pregnant women vaccinated with RIV4 versus IIV4 during the study
- b)
  - 1. EOM2.1. Proportions of infants born small-for-gestational age after RIV4 versus IIV4 vaccination.
  - 2. EOM2.2: Proportion of pregnant women with clinical chorioamnionitis after RIV4 versus IIV4 vaccination.
  - 3. EOM2.3: Proportion of women with preeclampsia or eclampsia after RIV4 versus IIV4 vaccination.

c)

1. EOM3.1: Proportion of infants with medically-attended events through 90 days of life after maternal RIV4 versus IIV4 vaccination.
2. EOM3.2: Frequency and description of SAEs in infants through 90 days of life after maternal RIV4 versus IIV4 vaccination.
3. EOM3.3 Proportion of infants with neonatal death after maternal RIV4 versus IIV4 vaccination.

d)

1. EOM4.1: Proportion of pregnant women achieving seroconversion at day 29 after RIV4 versus IIV4 vaccination [a Hemagglutination Inhibition Assay (HAI) titer  $\geq 1:40$  at day 29 if the baseline titer is  $< 1:10$  or a minimum four-fold rise in HAI titer if the baseline titer is  $\geq 1:10$ ) for each influenza vaccine antigen].
2. EOM4.2: Proportion of pregnant women with a seroprotective HAI titer ( $\geq 1:40$ ) post-vaccination at day 29 after RIV4 versus IIV4 vaccination for each influenza vaccine antigen.
3. EOM4.3: The maternal geometric mean HAI titer (GMT) pre and post-vaccination at day 29 after RIV4 versus IIV4 for each influenza vaccine antigen and the post/pre-vaccination ratio.

e)

1. EOM5.1: Proportion of infants with cord blood seroprotective HAI titer ( $\geq 1:40$ ) for each influenza vaccine antigen after maternal RIV4 versus IIV4 vaccination.
2. EOM5.2: Infant cord blood geometric mean HAI titer (GMT) for each influenza vaccine antigen after maternal RIV4 versus IIV4 vaccination.
3. EOM5.3: Ratio of cord blood to maternal influenza antibody titers at time of delivery for each influenza vaccine antigen after maternal RIV4 versus IIV4 vaccination.

## 4 STUDY DESIGN

### 4.1 Study Description

This study is a prospective, randomized clinical trial of approximately 430 pregnant women enrolled at Duke University Medical Center (Lead Contractor), Cincinnati Children's Hospital Medical Center (Contributing Contractor), and Boston Medical Center (Contributing Contractor). Pregnant women  $\geq 18$  years of age at  $\leq 34$  weeks gestation, will be enrolled and randomized 1:1 to receive either quadrivalent recombinant influenza vaccine (RIV4) or quadrivalent inactivated influenza vaccine (IIV4). The designated vaccine brands for this study are Flublok® quadrivalent (Sanofi) and quadrivalent Flulaval® (GSK) (comparator

IIV4). However, the choice of IIV4 vaccine administered will be based on availability from manufacturers prior to the 2019-2020 and 2020-2021 influenza seasons.

After vaccination, participants and their infants will be followed to assess adverse pregnancy and birth outcomes, maternal vaccine reactogenicity, immunogenicity, serious adverse events, and short-term infant outcomes. Maternal and infant outcomes will be collected by medical record review from enrollment through 90 days postpartum.

#### **4.2 Laboratory**

**Serologic studies** – We will evaluate pre- and post-vaccination serologic responses in both IIV4 and RIV4 groups. IgG levels will be measured for the specific viral strains included in the 2019-2020 and 2020-2021 quadrivalent influenza vaccines using hemagglutination inhibition assays at the Duke Regional Biocontainment Laboratory (RBL) Virology Unit. Venous blood (approximately 15 mL of blood) will be collected from each participant before and 29 (-7 to +14) days after vaccination. At Duke, maternal and infant cord blood (approximately 15mL of blood each) collection will be performed at delivery for serological analysis in both RIV4 and IIV4 vaccination groups. At the other sites, these samples (maternal and cord blood) will be collected during delivery only if feasible for similar serological analysis. An assessment of placental antibody transfer (maternal:cord antibody ratio) will be determined.

#### **4.3 Sample Size and Power**

Allowing for a 5% drop out rate and given an initial N=430, there should be approximately 408 pregnant women participants for evaluation. We assume that 15% of pregnant women will have adverse birth outcomes after vaccination with RIV4 or IIV4, based on national and CISA site estimates of preterm birth rates. We have selected a clinically meaningful noninferiority margin of 10%. Statistical calculations show that with a one-sided alpha of 0.025 and 204 subjects in each group across all study sites, there is approximately 81% power to reject the null hypothesis that RIV4 is inferior to IIV4 in the proportion of adverse birth outcomes.

#### **4.4 Randomization**

Participants will be randomized (1:1) to receive either RIV4 (Flublok® quadrivalent recombinant influenza vaccine) or IIV4 (quadrivalent inactivated influenza vaccine) using a permuted block randomization scheme stratified by study site (Duke, Cincinnati, Boston). The project statistician will generate permuted block randomization schemes which will be uploaded to REDCap. The randomization schedule will not be available to the study staff, so the next randomization allocation will not be known before randomization occurs. Following confirmation of study eligibility criteria during Visit 1, participant randomization will be through REDCap with treatment allocation recorded on the case report form (CRF).

In the event that REDCap is unavailable, manual randomization will occur through the use of envelopes. The project statistician will prepare 20 envelopes per gestational age group per site (total of 40 per site) that will use the same randomization strategy as the primary scheme embedded in REDCap. When an unblinded team member is informed of the gestational age group, he/she will pull the next envelope in order. In order to capture the allocation per subject, a separate form in REDCap will be used by the unblinded personnel to add the assignment. A log will need to be kept at the site capturing these instances.

We had planned to have gestational age as a stratification factor for randomization (<20 weeks,  $\geq$  20 weeks). Unfortunately, the setup in REDCap only drew from the <20 weeks randomization block. The benefits for randomization have been maintained, and we will evaluate secondary outcomes by site and gestational age to determine if specified analyses can adjust for this factor. The cell counts need to be 5 or greater to have reasonable results.

#### **4.5 Blinding**

This study is double-blinded, therefore study staff and participants will be blinded to randomization assignments. Trained, licensed staff will serve as unblinded vaccinators to administer either RIV4 or IIV4. All other study personnel involved in collection of memory aids, follow-up phone calls, and data collection, will be blinded to randomization arm. Laboratory staff will be blinded to randomization arm assignment.

The participant will receive documentation of receipt of influenza vaccine without specification of whether it was RIV4 or IIV4 vaccine to preserve blinding. In the event of individual participant clinical safety issues or overall study safety concerns, then blinding may be broken.

### **5 PARAMETERS OF ANALYSIS**

#### **5.1 Data Collection and Storage**

Data will be handled according to the Duke Vaccine and Trials Unit Standard Operation Procedure (SOP) (DVTU M010). Data will be captured on paper case report forms (CRFs) and entered into the REDCap database. Memory aid data may be entered directly into REDCap by the participant, if the participant chooses to use this method.

#### **5.2 Analytic Issues**

There are three study sites participating in the study and analysis of the primary objective will be stratified by site (Duke, Boston, Cincinnati) to account for this unit of randomization. All objectives will be stratified by site when applicable. There is one primary objective being evaluated, using a noninferiority hypothesis at the one-sided alpha 0.025 level. Otherwise, the alpha level will be set at two-sided alpha 0.05 for the secondary objectives and all exploratory objectives.

### **6 ANALYSIS POPULATIONS**

#### **6.1 Modified Intent-to-Treat (mITT):**

The mITT Population includes any participant that was enrolled, randomized into the study, and received study vaccine.

#### **6.2 Per Protocol (PP):**

The PP Population is a subset of the mITT Population excluding those participants with major protocol violations as determined by the study investigators (Appendix 1).

#### **6.3 Maternal Immunogenicity Population**

The Maternal Immunogenicity Population is a subset of the mITT Population that includes only pregnant women participants who received study vaccine, provide baseline and post-vaccination Visit 4 blood draws available for analysis within the protocol-defined time frame,

and with no major protocol violations affecting immunogenicity as determined by the study investigators.

The mITT Population is the primary analysis population for the safety and health outcomes analyses, with the PP Population as a confirmatory analysis population. The Immunogenicity Population is the primary analysis population for maternal immunogenicity outcomes (Exploratory Objectives 5); otherwise the mITT Population will be used for the Exploratory Objectives.

## 7 BASELINE DATA AND FLOW CHART

### 7.1 Presentation of Baseline Data

The following baseline information will be presented by treatment group, age, ethnicity, race and tobacco, marijuana or other substance use, gestational age at vaccination, study enrollment site, and influenza season of enrollment. Summary statistics (e.g., mean, standard deviation, median) will be presented for continuous variables. Categorical variables will be described with frequencies and percentages. Specific medical issues (i.e., hypertension, diabetes, and prior preterm birth) will also be presented.

### 7.2 Flow Chart

The number of enrolled participants will be presented in a flow chart by treatment group. The number of visits completed and missed will be presented, along with a breakdown of the three analysis populations.

## 8 ANALYSIS OF STUDY OBJECTIVES

### 8.1 Primary Objective

1. To compare the proportions of adverse birth outcomes in pregnant women vaccinated with RIV4 versus IIV4.
  - o *Research hypothesis: The proportion of pregnant women with adverse birth outcomes will be noninferior (not higher – based on the noninferiority margin) after receipt of RIV4 compared to IIV4.*

This objective will be assessed using a one-sided noninferiority test with the alpha level set at 0.025 (1-sided) and a noninferiority margin of 10%.

The null hypothesis assumes that RIV4 is inferior to IIV4 in regards to the proportion of pregnant women with adverse birth outcomes.

$$H_0: RIV4 - IIV4 \geq 0.10 \text{ (10\%)}$$

The alternative hypothesis states that RIV4 is noninferior to IIV4 in regards to the proportion of pregnant women with adverse birth outcomes.

$$H_a: RIV4 - IIV4 < 0.10 \text{ (10\%)}$$

The upper bound of a stratified (by study site) Newcombe binomial confidence interval (Yan and Su 2010) with Cochran-Mantel-Haenszel (CMH) weighting of the difference will be used to make this assessment.

A composite outcome for adverse birth outcome [defined by the occurrence of at least one of the following events: preterm birth, spontaneous abortion, fetal death or neonatal death] will be used as the primary study endpoint.

Definitions for the component of the primary outcome measures are as follows:

- Preterm birth- born alive at less than 37 weeks and 0 days gestation
- Spontaneous abortion (SAB)- pregnancy loss prior to 20 weeks 0 days
- Fetal death- intrauterine death of fetus at or after 20 weeks 0 days
- Neonatal death- infant death within first 28 days of life.

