5 STUDY SCHEDULE, PROCEDURES, & EVALUATIONS

5.1 Schedule of events

Pregnant women meeting the proposed eligibility criteria will be recruited. Written informed consent (will be obtained from study participants prior to conducting any study procedures. **Table 1** describes the proposed schedule of study visits with further details below.

Table 1. Study Visit Schedule									
Procedure	Screening Visit* Day -30 to 1	Visit 1 Day 1	Visit 2 Day 4 + 1	Visit 3 Day 9 + 3	Visit 4 Day 29 -7/+14	Visit 5 Day 43 + 7	Visit 6 Delivery	Visit 7 Postnatal Day 90 + 14	Unscheduled Visit
Type of contact	Chart Abstraction/ Clinic	Clinic	Phone/Text/ Email/Data Review	Phone/Text /Email/Data Review	Clinic	Phone/Text/ Email/Chart Abstraction	Hospital/ Chart Abstraction	Phone/Text/ Email/Chart Abstraction	Clinic
Informed consent & Medical Release of Information	Х								
Review Eligibility Criteria	Х	Х							
Demographic, Medical, and obstetric history	Х	Х							
Influenza Vaccination History	X	Х							
Vital signs (temperature, blood pressure, and heart rate)		Х							Х
Blood Sample Collection		Х			Х		X ¹		
Randomization and Vaccination		Х							
Obtain immediate adverse event information		Х							
Dispense memory aid		Х							
Dispense study supplies		Х							
Complete Memory aid form (REDCap or paper)		Х	Х	Х					
Concomitant medications/vaccinations	Х	Х	Х	Х	Х	Х	Х	Х	Х
Obtain solicited adverse events		Х	Х	Х					
Obtain unsolicited adverse events		Х	Х	Х					Х
Obtain serious adverse event information		Х	Х	Х	Х	Х	Х	Х	Х
Infant data collection								Х	

¹Cord blood and maternal blood collection at Visit 6 will be optional and collected when feasible by the site.

Screening Visit, Study Day -30 to 1 (Chart Abstraction & Clinic Visit – may occur simultaneously with Visit 1)

- Obtain written informed consent and release of medical record information
- Review and confirm study eligibility
- Obtain information on preferred method of contact for follow-up (telephone or email reminder or text reminder)
- Obtain demographic data
- Obtain influenza vaccination history
- Obtain medical history (e.g. chronic hypertension, diabetes, autoimmune disorder), obstetric history (e.g. parity, prior preterm birth, low birthweight, small for gestational age), and current pregnancy status (e.g. gestational diabetes, gestational hypertension, placenta previa, estimated due date)
- Obtain concomitant medication use

Visit 1, Study Day 1 - Screening, Enrollment, and Vaccination (Clinic Visit)

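### The primary noninferiority interval is valid but adjusts for site only; pre-specifying adjustment for prior preterm birth, hypertension and diabetes would recover a modest amount of precision at almost no cost

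*SAP*

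**What the plan says.** **Primary analysis.** SAP 8.1 and Protocol 7.3.3 use the same decision rule: "The upper bound of a stratified (by study site) Newcombe binomial confidence interval (Yan and Su 2010) with Cochran-Mantel-Haenszel (CMH) weighting of the difference" is compared with 10%. SAP 5.2 repeats that the stratification is by site and adds no covariate.

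**SO1 (preterm birth).** SAP 8.2 uses an exact Mantel-Haenszel test stratified by site, with a site-adjusted odds ratio. Protocol 7.3.4 has the same test with a site-adjusted relative risk.

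**Baseline data.** The Screening Visit in Protocol 5.1 takes medical history, including chronic hypertension and diabetes, and "obstetric history (e.g. parity, prior preterm birth, low birthweight, small for gestational age". Gestational diabetes and gestational hypertension are listed separately, under current pregnancy status. Screening precedes randomisation. SAP 7.1 then states: "Specific medical issues (i.e., hypertension, diabetes, and prior preterm birth) will also be presented". No analysis uses these variables.

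**Other adjustment.** SAP 10 and Protocol 7.3.16 allow gestational age as a covariate for secondary outcomes only, if the stratification error leaves an imbalance and cell counts are at least 5. The sensitivity analyses in SAP 9 cover treatment received and immunogenicity violations.

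**The concern.** The 15% composite rate in SAP 4.3 is "based on national and CISA site estimates of preterm birth rates", so preterm birth is expected to drive the endpoint. Obstetric history, hypertension and diabetes are then natural candidates for predicting it, and the SAP itself singles them out for the baseline table. An analysis that ignores prognostic baseline variables leaves their chance imbalance in the estimate as noise.

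Two things are at stake. The design has power only just above 80%, so some precision from data already held is worth having. And if the baseline table shows the arms differing on prior preterm birth, readers will ask for an adjusted primary result. The plan has none, so any answer would be post hoc.

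**Working it through.** **Inputs from SAP 4.3.** "with a one-sided alpha of 0.025 and 204 subjects in each group across all study sites"; 15% in each arm ("We assume that 15% of pregnant women will have adverse birth outcomes after vaccination with RIV4 or IIV4"); margin 10 points; "Allowing for a 5% drop out rate and given an initial N=430", and 430 × 0.95 = 408.5, or about 408 evaluable. Stated power is about 81% (SAP) and at least 80% (Protocol 7.2).

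**Step 1: reproduce the stated power.**
- SE = √(2 × 0.15 × 0.85 / 204) = √0.00125 = 0.03536.
- Power = Φ(0.10 / 0.03536 − 1.960) = Φ(0.868) = 80.7%.
- 95% half-width = 1.960 × 3.536 = 6.93 points.
- Exact enumeration with the unstratified Newcombe bound gives 80.4%. The plan's figure reproduces.

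**Step 2: is the planned interval valid?** With a true difference of +10 points and control rates of 10, 15 and 20%, the exact one-sided error of the unstratified Newcombe bound is 0.0255, 0.0259 and 0.0258. That is close to the nominal 0.025.

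**Step 3: effect of adjustment.** If the covariates explain a share R² of outcome variance, the SE becomes SE × √(1 − R²), and 408 women carry the information of 408 / (1 − R²). R² is an assumption, because the documents give nothing from which to derive it.

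| R² (assumed) | SE (points) | 95% half-width (points) | Power | Equivalent total N |
|---|---|---|---|---|
| 0 | 3.54 | 6.93 | 80.7% | 408 |
| 1% | 3.52 | 6.89 | 81.1% | 412 |
| 5% | 3.45 | 6.75 | 82.7% | 429 |
| 10% | 3.35 | 6.57 | 84.7% | 453 |

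**Step 4: what could give such an R²?** These are illustrative assumptions for prior preterm birth, hypertension and diabetes, in that order. Simulated power is from 4,000 trials per scenario, with equal-sized sites and pooled Wilson limits as an approximation to the stratified interval.

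| Scenario | Prevalence | Risk ratio | R² | Simulated power, site-adjusted Newcombe | Simulated power, standardised logistic |
|---|---|---|---|---|---|
| Low | 8 / 5 / 5% | 2.0 / 1.5 / 1.3 | 1.4% | 80.4% | 81.2% |
| Middle | 10 / 10 / 8% | 2.5 / 2.0 / 1.5 | 4.6% | 80.3% | 82.5% |
| High | 15 / 15 / 10% | 3.0 / 2.5 / 2.0 | 10.5% | 80.9% | 84.8% |

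Simulated one-sided error at the margin (Newcombe v standardised) was 0.024 v 0.027, 0.025 v 0.023 and 0.031 v 0.033. In the high scenario both exceed 0.025 because capping individual risks put the true difference slightly below 10 points. Adjustment shows no material cost in error rate.

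**Step 5: size of the removable noise.** The part of the estimated difference due to chance imbalance in these factors has SD √R² × SE: about 0.4 (low), 0.8 (middle) and 1.15 (high) points, against a total SE of 3.5 points.

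**Step 6: can the model be fitted?** Expected events are 408 × 0.15 ≈ 61. Arm (1), site (2), three-level obstetric history (2), hypertension (1) and diabetes (1) make 7 terms, or roughly 9 events per term.

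**The case against.** The strongest reply is that nothing is broken. Randomisation and the primary interval are stratified by the same factor, the stated power reproduces without covariates, and a 95% interval already allows for chance imbalance in every baseline variable. The gain rests on prevalences and risk ratios that the documents do not contain, and at the low end it is under one point of power. In a separate simulation of 2,000 trials per scenario with no true difference, the planned and adjusted analyses reached different conclusions in only about 3, 6 and 7% of trials (low, middle, high). All of this stands, and it limits the point to efficiency.

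A reader might go further and infer that the site-only interval is biased, or that an imbalance in prior preterm birth would readily decide the trial. The second inference has some surface appeal: with 31/204 events on IIV4, the unstratified Newcombe bound is 9.67% at 36 RIV4 events (pass) and 10.20% at 37 (fail). The documents support neither inference. Randomisation protects the estimate. Those counts describe one control result, and only an uncommon imbalance would use up much of that room. With prior preterm birth assumed in 8 to 15% of women and a risk ratio of 2 to 3, a 1-SD imbalance moves the difference by 0.37 to 0.82 points, against an SE of 3.54.

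It would also be too broad to say that preterm birth is adjusted for site in every circumstance. SAP 10 allows gestational age for secondary outcomes, though it covers none of these three factors and does not reach the primary endpoint.

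Practical cautions also stand. History is self-reported and chart-verified only where feasible (Protocol 4.3), and gestational diagnoses depend on when a woman enrols. The amended text must therefore define the covariates and deal with missing values.

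**Conclusion.** The point holds as a modest, inexpensive gain in precision. The planned primary interval is valid, with one-sided error near 0.025, and the trial meets its stated power on its own inputs. What is given up is the information in baseline variables that the plan already collects and tabulates.

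If those variables explain 1 to 10% of outcome variance, power goes from about 80.7% to about 81 to 85%, and the half-width from 6.9 points to between 6.9 and 6.6. The range is an assumption; the true gain could be near zero if the factors are weakly prognostic here. The second benefit does not depend on R²: an adjusted primary result would be fixed in advance.

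**What to change.** Before unblinding, amend SAP 8.1, and Protocol 7.3.3 to match:

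- **Primary analysis.** A standardised (marginal) risk difference from a logistic model with arm, site, obstetric history (nulliparous; parous without prior preterm birth; parous with prior preterm birth), hypertension and diabetes. Take hypertension and diabetes as recorded before randomisation, and state which diagnoses count.
- **Decision rule.** Use a robust standard error and compare the upper 97.5% bound with the unchanged 10% margin. The estimate must stay on the risk-difference scale, because an adjusted odds ratio would not correspond to that margin.
- **Missing history.** State a simple rule, for example a missing category.
- **Sensitivity analysis.** Keep the site-stratified Newcombe interval in this role. Giving the roles the other way round would leave the decision rule as it is and would not recover the precision.
- **SO1.** Add the same standardised risk difference beside the exact site-stratified test. The gestational-age provision in SAP 10 can stay as it is.

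The cost is a paragraph in each document and a few lines of code. No new data, visits or participants are needed.
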